- **Feasibility and tolerability of the interventions** assessed by enrollment and retention numbers, protocol related adverse events (AE's), and questionnaires assessing satisfaction, quality of life and mood.
- Adherence to interventions assessed both with self-report and with the use of a smartphone application in conjunction with continuous glucose monitoring.

Secondary Outcomes:

- Weight (scale) and body composition (DXA) obtained at baseline (prior to the weight loss intervention), at 12 weeks (following the weight loss intervention), and at a 6mo follow-up time point.
- Physical activity assessed by accelerometry
- Free-living sleep patterns assessed by wrist actigraphy
- Objective (in-laboratory) sleep recording using Compumedics Inc Siesta digital sleep recorders
- Meal timing and energy intake assessed by photographic food records
- Patterns in 24h glucose assessed by continuous glucose monitors over 7 days before and after the weight loss intervention
- Questionnaire based measures of appetite
- HqbA1c and lipids
- Resting metabolic rate and nocturnal energy metabolism by indirect calorimetery

B. Description of Population to be Enrolled:

Inclusion criteria.

- Adult males and females with a BMI of 27-45 kg/m² and weight stable over the previous 6 months;
- Age, 18-50 years old;
- Passing medical and physical screening, and analysis of blood and urine screening samples:
- Typical eating duration >12 hours per day (assessed by questionnaires);
- Own a smartphone
- Reside or work within approximately 30 minutes driving distance of CU-AMC (potential
 participants living outside of this driving distance could be included in the study at the PIs
 discretion).
- For participants in the optional Reproductive Hormone Sub-study: females, age 18-40, with regular menstrual cycles (between 18-40 days).

Exclusion criteria.

- Pregnancy or lactation for women (women who are >6 months postpartum with no plans of becoming pregnant in the next year and who are not currently lactating can be included; oral contraceptives will be allowed if medication has been consistent for the prior 6 months)
- Postmenopausal women (menopausal status will be assessed during the history and physical, with requirement of self-reported regular menstrual cycles for the last year; women who have undergone hysterectomy but with ovaries in place who continue to have regular menstrual symptoms can be included)

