Informed consent, medical evaluation and labs. After telephone screening, interested participants will be scheduled for an in-person screening visit to determine eligibility. After providing written informed consent, participants will undergo the following evaluations: medical history and physical examination (including measurement of weight, height, BP, HR), and screening tests (Hemoglobin A1C, lipid panel, comprehensive metabolic panel, TSH and pregnancy test). Patients who have had these tests done and found to be normal within the last 6 months may submit the results and forego the screening labs. If any screening test is abnormal the participant will be informed immediately and asked to follow-up with his/her doctor.

Questionnaires. Participants will be asked to complete a meal pattern assessment questionnaire to assess for components of night eating syndrome, as well as the Munich Chronotype Questionnaire³⁷ to evaluate chronotype. In addition, participants will complete the Binge Eating Scale (BES), a 16-item survey used to identify the presence and severity of binge eating behaviors³⁸.

Resting energy expenditure (REE): REE will be measured after an overnight fast using standard indirect calorimetry³⁹ (Parvo Medics TrueOne 2400, Salt Lake City, UT).

To enhance feasibility of recruitment, participants can complete the informed consent and history and physical exam during a separate visit from the screening/baseline procedures that require fasting (blood draw and REE measurement). In addition, participants may undergo DXA testing at the screening visit if screening is done within 4 weeks of the intervention start date.

Baseline Assessments (7-day period no less than 4 weeks prior to starting the weight loss intervention).

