Appetite will be measured using visual analog scales (VAS) before and after each meal for the final 3 days of cell phone meal tracking as previously described⁴³ and as used by our group in prior studies^{34,44,45}.

Free-living Sleep Patterns: Subjects will complete several validated questionnaires to evaluate aspects of daytime sleepiness, sleep quantity/quality, and sleep timing: Berlin Questionnaire, Epworth Sleepiness Scale⁴⁶, Pittsburgh Sleep Quality Index⁴⁷, and Morningness -Eveningness Questionnaire⁴⁸. Each subject will also keep a written log of sleep/wake times and wear a wrist activity and light exposure recorder to document free-living sleep/wake patterns for 7 continuous days (Actiwatch Spectrum, Philips Respironics, Bend, OR).

Mood, quality of life and eating behaviors: Quality of life (QOL) will be assessed with the RAND-36^{49,50} physical and mental health component summary score. Mood state will be assessed with the Profile of Mood States 40 Item Questionnaire (POMS-40)⁵¹⁻⁵³. Eating behaviors will be assessed with the Three Factor Eating Questionnaire (TFEQ)⁵⁴.

Body Weight and Composition Assessment. Body weight and composition will be measured using a digital scale and dual energy x-ray absorptiometry (DXA, Hologic Inc., Bedford, MA).

Resting energy expenditure (REE): the resting metabolic rate measurement would be repeated in any participant presents with significant weight gain or loss (+/-2kg) between the time screening and the time of baseline assessments. Otherwise, the REE measurement performed at the time of screening will be considered as the baseline.

Optional In-laboratory assessments:

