Following completion of the baseline assessments, all participants will receive a 9-month groupbased behavioral weight loss program, with randomized groups meeting separately. Participants will be randomized 1:1 to RCD+TRF or RCD. Groups will be held at the AHWC and will be taught by an RD with experience in leading group-based behavioral weight loss interventions. In case of situations in which in-person classes cannot be held (i.e., due to concern for transmission of disease during the COVID-19 global pandemic), meetings will be held virtually via Zoom. Zoom is a HIPAA compliant web and video conferencing platform. All participants will be provided with a link to join the meeting and instructions regarding optimal conditions in which to join the meeting (i.e., a quiet location with minimal distractions and ability to devote full attention to the meeting). Group meetings will be moved back to in-person when it is deemed safe to do so. Group meetings will take place weekly during weeks 1-12, then monthly between months 4 and 9. Groups will meet separately to maintain intervention integrity. Classes will last ~60 minutes and the curriculum will be delivered using a mix of large group discussion, small breakout discussions, visual demonstrations, and written exercises. The programs will fulfill all recommendations for behavioral interventions outlined in current guidelines³². Current guidelines suggest the most effective behavioral treatment for obesity is a high-intensity, comprehensive weight loss intervention provided in individual or group sessions by a trained interventionist with principle components of a moderately reduced calorie diet, increased PA, and behavioral support to facilitate adherence 32. Curriculum will be based on the Colorado Weigh behavioral weight loss program, which uses a skills-based approach and cognitive behavioral strategies for lifestyle modification with a dietary focus on daily caloric restriction^{57,58}. The Colorado Weigh curriculum includes topics addressing the importance of exercise for weight loss. Specifically, the recommendations are for participants to achieve 150 min/wk of exercise, but exercise will not be supervised. Curriculum for RCD+TRF will be developed by [name], with input from a registered dietitian and will feature similar weekly themes as RCD, but modified to focus on support specific to TRF.

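### The baseline week has a four-week minimum gap before the intervention and no maximum, so the 12-week weight change spans at least 16 weeks as written and the screening-DXA allowance is almost unusable

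*Combined protocol and SAP*

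**What the plan says.** In Section IV.C, the heading over the Baseline Assessments times them as a "7-day period no less than 4 weeks prior to starting the weight loss intervention". Among the items under that heading is: "Body weight and composition will be measured using a digital scale and dual energy x-ray absorptiometry". Weight and DXA have no separate date there. The outcome list in Section IV.A says only that they are "obtained at baseline (prior to the weight loss intervention), at 12 weeks (following the weight loss intervention"), which sets no window.

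The paragraph just before that heading allows an alternative for DXA: "participants may undergo DXA testing at the screening visit if screening is done within 4 weeks of the intervention start date".

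Two other statements fix the order of events. The resting energy expenditure item repeats that test after "significant weight gain or loss (+/-2kg) between the time screening and the time of baseline assessments", so screening comes before baseline. The behavioral program then starts after baseline: "Following completion of the baseline assessments, all participants will receive a 9-month groupbased behavioral weight loss program". Allocation is the same for everyone: "Participants will be randomized 1:1 to RCD+TRF or RCD".

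Section IV.F treats 12-week weight change as the primary outcome for sample size and analysis, although Section IV.A lists weight as secondary. It states 80% power for a 3.5 kg difference with 24 per arm.

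**The concern.** A baseline is normally tied to the start of treatment by an upper limit. Here the limit runs the other way: staff following the text would schedule the baseline week early, and nothing would stop it from being very early. The interval labelled 12 weeks would then include a stretch in which no one was treated, of a length that can differ between participants.

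Two things are at stake. The first is precision: weight movement between baseline and start enters every change score as noise, and the within-arm change no longer describes 12 weeks of program. The second matters more for a pilot. Aim 1b and Section IV.F use this trial's variability estimates to size the large trial, so noise from an avoidable gap would carry into that calculation.

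The diet, CGM and activity baselines share the same open window.

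**Working it through.** **1. Interval between the two weights.** Inputs: gap of at least 4 weeks (Baseline Assessments heading); 12-week intervention; post-intervention visit within 3 weeks afterwards (Section IV.C, Post-intervention assessments).

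- Literal text: at least 4 + 12 = 16 weeks, or 4 + 12 + 3 = 19 if the post-visit falls at the end of its window. There is no maximum. At 16 weeks, 4/16 = 25% of the interval is untreated, and it is 16/12 = 1.33 times the nominal length.
- With an upper limit of 4 weeks instead: 12 to 16 weeks, or up to 19 with the latest post-visit.

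**2. Compatibility with the DXA allowance.** Let S and B be the weeks from screening and from baseline to the start. The heading gives B ≥ 4. The order of visits gives S ≥ B. The DXA allowance needs S ≤ 4. All three hold only at S = B = 4. With B ≤ 4, any S from B to 4 works.

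**3. Other possible limits.** Section IV.F makes completion of outcome measures within 2 weeks of the indicated time points a criterion for modifying the intervention. This is a feasibility threshold around whatever time point is indicated, and it does not cap the baseline gap.

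**4. The plan's own power figure.** Inputs from Section IV.F: SDs 3.7 and 4.2 kg, 24 per arm, alpha 0.05 (two-sided assumed, since sidedness is not stated), 80% power.

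- Variance sum: 3.7² + 4.2² = 13.69 + 17.64 = 31.33. SE = √(31.33/24) = 1.143 kg.
- Normal approximation: (1.960 + 0.842) × 1.143 = 3.20 kg. Noncentral t with Welch degrees of freedom: 3.27 kg.
- Power at 3.5 kg: 86.5% (normal) or 85.0% (t), against the stated 80%.

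The stated 3.5 kg is therefore not reproduced. An SD of 4.2 in both arms gives 3.47 kg, and 21 per arm gives 3.51 kg, so one of these may be its source. The difference is on the conservative side and is separate from this point.

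**5. Illustration of added noise.** The documents give no drift figure. Assume that drift between baseline and start is independent of later change and has SD d in each arm. Each arm's SD becomes √(SD² + d²), and the variance sum becomes 31.33 + 2d². The required sample size of a later trial is proportional to that sum.

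| d (kg, assumed) | SDs (kg) | Detectable difference (kg, t) | Power at 3.5 kg (t) | Variance sum vs no drift |
|---|---|---|---|---|
| 0 | 3.70 / 4.20 | 3.27 | 85.0% | 1.00 |
| 0.5 | 3.73 / 4.23 | 3.30 | 84.5% | 31.83/31.33 = 1.02 |
| 1.0 | 3.83 / 4.32 | 3.37 | 82.8% | 33.33/31.33 = 1.06 |
| 1.5 | 3.99 / 4.46 | 3.50 | 80.1% | 35.83/31.33 = 1.14 |
| 2.0 | 4.21 / 4.65 | 3.66 | 76.3% | 39.33/31.33 = 1.26 |

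**The case against.** The strongest reply is that this is a drafting slip. The DXA sentence treats closeness to the start as desirable, so the authors probably meant an upper limit, and the 16-week interval exists only on paper. That is likely. It does not remove the point, because the operative text would then instruct staff to do the opposite of what was meant.

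A second reply is that the four-week rule attaches to a 7-day period, which suits the free-living recordings, and that weight is caught only because it is listed under the same heading. This is correct: the date of the baseline weight is inferred from its place in the document. But no other date is given, so the analysis baseline is left undefined.

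A reader might also draw four stronger conclusions that the documents do not support.

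- *The plan requires DXA within 4 weeks of the start.* The sentence is a conditional permission for doing DXA at screening. It does not limit a DXA done at the baseline visit.
- *The plan expects weight to shift by 2 kg before treatment.* The 2 kg figure triggers a repeat metabolic-rate test and covers screening to baseline, not baseline to start. Used as a drift SD, it would imply that about 32% of participants move by more than 2 kg (normal, mean zero), a change the protocol calls significant. Entry also requires stable weight over the previous 6 months (Section IV.B). The upper end of the table is therefore a generous bound.
- *The gap biases the treatment comparison.* It falls on both arms of a 1:1 randomization, and nothing in the documents makes it differ by arm.
- *The trial loses its stated power.* At 3.5 kg this happens only when the assumed drift SD exceeds about 1.5 kg. Aim 1b already says the pilot is not powered for weight loss differences.

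**Conclusion.** The rule is wrong as written and should be corrected. It sets a minimum where a maximum is needed, and it leaves the neighbouring DXA allowance usable only at exactly 4 weeks. On the literal text, the baseline-to-12-week interval is at least 16 weeks, with at least 4 untreated and no upper bound.

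The statistical consequence is added noise in the change scores and in the SDs meant for the future trial, and a blurred within-arm 12-week change. Its size is unknown. Over an assumed drift SD of 0.5 to 2 kg, the detectable difference rises by 0.03 to 0.39 kg from 3.27 kg, and a sample size based on the inflated SDs would be about 2% to 26% larger. These figures assume independent drift of equal SD in both arms and 24 evaluable participants per arm.

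The documents do not show that participants were in fact measured this early.

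**What to change.** - Reconcile the two windows in Section IV.C by changing *no less than* to *no more than* 4 weeks before the intervention, which matches the screening-DXA allowance.
- State in Section IV.F that the analysis baseline weight is the last in-person study-scale weight in that window before the intervention starts.
- For participants already enrolled, report the baseline-to-start gap by arm.

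A weigh-in at the first class is a tempting substitute but a poor one. Classes are held separately by arm, so that weight would be taken after randomization. They may be on Zoom, where no study scale is available. It would also put weight and DXA on different dates.

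The cost is a wording correction, one added definition and a slightly tighter scheduling window.
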